11.8.2. Blinded Data Monitoring Committee

A bDMC will review data from an initial subset of at least 8 subjects completing Period 3 to determine if the duration of Period 3 may be adjusted in order to adequately capture primary endpoints while maximizing subject retention. The subjects to be evaluated for this purpose will include at least 4 subjects ≥ 12 years old and at least 2 subjects 2-11 years old. A charter will be prepared to further describe membership and the roles and responsibilities of the bDMC.

12. STATISTICS

12.1. Number of Subjects

Approximately 40 subjects will enter the Open-label Lead-in Period (Period 2), so that at least 32 are randomized and complete the Withdrawal Period (Period 3). Sixteen evaluable subjects per arm provides at least 90% power to show superiority of ADV7103 over placebo in the proportion of subjects who develop hyperchloremic metabolic acidosis up to Day 6. This calculation assumes that approximately 85% of placebo subjects and 15% of ADV7103 subjects will develop hyperchloremic metabolic acidosis. Significance will be assessed at the 2-sided 5% level.

Randomization will be stratified according to the following age categories:

- 6 months - 23 months old
- 2 - 11 years old
- ≥ 12 years old.

12.2. Analysis Sets

The Intent-to-Treat (ITT) analysis set is defined as all randomized subjects in Period 3.

The Modified Intent-to-Treat (mITT) analysis set is defined as all subjects in the ITT Analysis Set who received study product in Period 3 and who have both a baseline and at least one post baseline efficacy assessment in Period 3.

The Per-Protocol (PP) analysis set is defined as all subjects in the mITT analysis set who have no major protocol deviations affecting the assessment of efficacy. Membership of the PP analysis set will be confirmed prior to unblinding the data.

The ITT, mITT, and PP analysis sets will be analyzed per planned study product assignment.

The Safety analysis set is defined as all subjects who receive at least one dose of study product in any period or phase. The Safety analysis set will be analyzed per actual study product received.

12.3. Primary Analysis

The primary endpoint is the proportion of subjects with at least one episode of metabolic acidosis up to Day 6. All non-missing serum bicarbonate measurements from first study product dose in Period 3 to Day 6 (≤ 24 hours post-last dose) or early discontinuation will be considered.

The primary analysis will be based on the ITT set. The primary study product comparisons will be made using the two-sided Cochran-Mantel-Haenszel (CMH) test stratified by age category.

12.4. Secondary Analyses

The proportion of subjects with significant hypokalemia up to Day 6 of Period 3 will be similarly analyzed with a CMH test.

The proportion of subjects who fail to maintain serum bicarbonate levels ≥ 18 mEq/L for subjects ≥ 4 years old or ≥ 17 mEq/L for subjects < 4 years old up to Day 6 will be compared

with the CMH test. Time to first episode of metabolic acidosis and time to first episode of hypokalemia will be compared with a log-rank test. Mean change in serum bicarbonate level, mean change in serum potassium level, mean change in urine calcium/creatinine ratio, and mean change in urinary citrate/creatinine ratio will be compared at a last observation carried forward (LOCF) endpoint with an analysis of covariance model, having study product assignment and age category as factors and baseline as a covariate.

Descriptive summaries will be provided by study product and overall for the Open-label Lead-in Period (Period 2).

Safety data will be summarized in the safety analysis set by study product and over time, for each period separately and overall.

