6.2.2.2. Period 2 - Stabilization Phase

Once two consecutive serum bicarbonate levels are 21-27 mEq/L (inclusive) for subjects ≥ 4 years old and 20-26 mEq/L (inclusive) for subjects < 4 years old on the same ADV7103 dose, the subject will remain on this ADV7103 dose for 6-8 weeks (ie, Stabilization Phase of Period 2). During this phase, the subject will be monitored, with serum bicarbonate and potassium levels obtained every 2 weeks (or more often if determined by the Investigator in consultation with Medical Monitor). At the end of the Stabilization Phase (ie, after 6-8 weeks post titration), the Stabilization Visit (ie, Visit 2) will take place at the investigational site or in the subject's home and via telehealth, with the subject remaining on her/his stable dose of ADV7103. At this time, the Investigator will assess the eligibility of the subject for the Randomized, Double-blinded Withdrawal Period (Period 3).

Subjects eligible for randomization must meet all of the following criteria:

- a stable ADV7103 dose, for a minimum of six weeks;
- serum bicarbonate level within target range and serum potassium level ≥ 3.0 mEq/L, both at Visit 2;
- serum bicarbonate level is maintained in the corresponding age-specific normal range for at least 80% of available results obtained during the Stabilization Phase of Period 2;
- serum potassium level ≥ 3.0 mEq/L for at least 80% of available results obtained during the Stabilization Phase of Period 2;
- acceptable safety and tolerability as determined by the Investigator at the enrolling site.

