6.3.2. Secondary Endpoints

- Proportion of subjects with 2 consecutive serum bicarbonate levels below the LLN for age during the Withdrawal Period;
- Proportion of subjects developing new onset hypokalemia during the Withdrawal Period. Hypokalemia is defined as a serum potassium level < 3.5 mEq/L.
- Time to metabolic acidosis during the Withdrawal Period;
- Time to new onset hypokalemia during the Withdrawal Period;
- Proportion of subjects with both metabolic acidosis and new onset hypokalemia during the Withdrawal Period;
- Mean urinary calcium/creatinine ratio associated with Visit 1, Visit 2;
- Mean change in urinary calcium/creatinine ratio during the Withdrawal Period;
- Mean urinary citrate/creatinine ratio associated with Visit 1, Visit 2;
- Mean change in urinary citrate/creatinine ratio during the Withdrawal Period;

- Frequency and severity of all adverse events (AEs), TEAEs, and all study product-related AEs;
- Frequency of SUSARs;
- Frequency of hyperkalemia;
- Frequency of serum potassium levels < 3.0 mEq/L;
- Frequency of serum potassium levels < 3.5 mEq/L;
- Changes in other serum and urine safety laboratory results from SOC baseline;
- Frequency of urine pH > 8.5 in Periods 1, 2, and 3.

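### The hypokalemia proportion and time-to-hypokalemia tests omit baseline potassium: they are valid but may lose power, by an amount the documents do not fix

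*Combined protocol and SAP*

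**What the plan says.** Section 12.4 gives the hypokalemia proportion the same test as the primary endpoint: "The proportion of subjects with significant hypokalemia up to Day 6 of Period 3 will be similarly analyzed with a CMH test". Section 12.3 stratifies that test by age category and nothing else. For the time-to-event endpoints Section 12.4 says: "Time to first episode of metabolic acidosis and time to first episode of hypokalemia will be compared with a log-rank test". It names neither strata nor a covariate.

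The same section compares mean changes, including the change in serum potassium, by analysis of covariance "having study product assignment and age category as factors and baseline as a covariate".

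The endpoint list in Section 6.3.2 fixes the line: "Hypokalemia is defined as a serum potassium level < 3.5 mEq/L". The threshold for randomization is lower. Section 6.2.2.2 asks for "serum potassium level ≥ 3.0 mEq/L for at least 80% of available results obtained during the Stabilization Phase of Period 2", and for at least 3.0 mEq/L at Visit 2, so starting values may lie on either side of 3.5. Potassium is part of the chemistry panel drawn before the first blinded dose (Sections 10.2.11.2 and 10.3.3.1).

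Section 12.1 sizes the trial on acidosis alone. No hypokalemia rate, potassium standard deviation or power for a hypokalemia endpoint appears anywhere.

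**The concern.** The event is crossing a fixed line from a starting point that differs between subjects. A subject who starts at 3.6 mEq/L needs a fall of just over 0.1; one who starts at 4.5 needs more than 1.0. Baseline potassium is therefore likely to predict the event within each arm. With 16 per arm, chance imbalance in it adds noise that neither planned test removes.

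The plan treats baseline potassium as worth adjusting for on one potassium endpoint and leaves it out of two others. Section 12.5 places the secondary efficacy endpoints under sequential gatekeeping, so a missed secondary result can also close the tests that follow it. At stake is the chance of showing a real difference, not type I error.

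**Working it through.** **1. The plan's own figure.** Section 12.1 states: "Sixteen evaluable subjects per arm provides at least 90% power to show superiority of ADV7103 over placebo", assuming that "approximately 85% of placebo subjects and 15% of ADV7103 subjects will develop hyperchloremic metabolic acidosis", with a two-sided 5% level. The pooled z approximation gives

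power = Φ{[0.70·√16 − 1.96·√(2·0.5·0.5)] / √(0.85·0.15 + 0.15·0.85)} = Φ{(2.80 − 1.386)/0.505} = Φ(2.80) = 99.7%.

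Fisher's exact test gives 98.4%. The stated figure is correct as a lower bound, but it concerns acidosis. The same formula at illustrative hypokalemia rates (assumptions) gives 62.9% for 70% v 30%, 64.9% for 60% v 20%, and 42.4% for 50% v 20%. A contrast weaker than the one assumed for acidosis would leave room for a gain.

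**2. Gain from adjustment, all starting values at or above 3.5.** Every potassium input is an assumption. Model: K on day j = b − s·j/6 + noise, j = 1 to 6; event = any K below 3.5; 32 subjects; age strata 4/10/18; mean b 4.1 before selection; 1,000 to 1,500 trials per row. CMH by age was compared with a logistic score test on baseline potassium and age, and log-rank with a Cox score test on baseline potassium. Critical values were recalibrated to 5% under the null. AUC is the discrimination of baseline potassium within placebo.

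| SD of b / noise / s | Fall, placebo / active | Event rate, placebo / active | AUC | Proportion: CMH → adjusted | Time: log-rank → adjusted |
|---|---|---|---|---|---|
| 0.20/0.20/0.40 | 0.7/0.2 | 66%/29% | 0.67 | 58→57% | 58→59% |
| 0.30/0.30/0.30 | 0.6/0.0 | 65%/27% | 0.71 | 57→64% | 53→56% |
| 0.30/0.15/0.40 | 0.7/0.2 | 61%/25% | 0.75 | 56→60% | 57→59% |
| 0.35/0.20/0.30 | 0.7/0.2 | 64%/28% | 0.81 | 57→67% | 55→61% |
| 0.40/0.20/0.20 | 0.7/0.2 | 62%/26% | 0.85 | 51→71% | 47→60% |
| 0.40/0.10/0.10 | 0.7/0.2 | 57%/16% | 0.95 | 72→96% | 70→94% |
| 0.40/0.10/0.10 | 0.6/0.2 | 48%/15% | 0.95 | 52→82% | 53→82% |
| 0.35/0.20/0.30 | 0.9/0.1 | 76%/22% | 0.80 | 90→95% | 87→93% |
| 0.30/0.15/0.30 | 1.1/0.0 | 88%/13% | 0.83 | 100→100% | 100→100% |

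The calibrated gain on the proportion runs from about −2 to +30 points.

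**3. Type I error.** Before recalibration the adjusted score tests rejected in about 4 to 7% of null trials, and recalibration removed up to about 6 points of apparent gain. A Firth penalized likelihood-ratio test behaves better. With age strata 20/10/2, five daily samples and 400 replicates, it rejected in 2.0 to 4.2% of null trials, against 3.0 to 5.2% for CMH. A gain from that test is not size inflation.

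**4. CMH → Firth, no stopping at acidosis** (Monte Carlo error about 2.5 points near 50%), for placebo falls of 0.4 and 0.6:
- entry at 3.0 or above, baseline SD 0.35, noise 0.15: 43→64% and 77→93%;
- entry at 3.0 or above, SD 0.45, noise 0.20: 26→41% and 59→80%;
- all at 3.5 or above, SD 0.35, noise 0.15: 54→69% and 91→98%;
- all at 3.5 or above, SD 0.45, noise 0.20: 35→45% and 64→80%.

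With SD 0.25 and noise 0.25 the gain was 3 to 8 points. With a fall of 0.9 it was 0 to 8.

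**5. Stopping at acidosis.** Under Section 6.2.3 a subject with confirmed acidosis leaves blinded product and restarts active ADV7103, and Section 12.1 expects about 85% of placebo subjects to reach acidosis. Four settings with all baselines at 3.5 or above and no stopping gave 49→62%, 41→51%, 86→97% and 71→85% (500 replicates, error about 2 points). With 85% of placebo subjects stopping on days 2 to 5 (uniform, assumed), the same settings gave 26→32%, 19→20%, 53→62% and 38→45%, gains of 1 to 9 points. Larger falls with stopping gave 6 to 15.

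**The case against.** The strongest reply is that nothing is broken. CMH and log-rank are valid in a randomized comparison, and the CMH strata match the randomization strata. Section 12.4 already contains one baseline-adjusted potassium comparison, the analysis of covariance of mean change. A model with product, age and baseline terms in 32 subjects gives a conditional effect that is harder to explain. Section 4.3.1 names hypokalemia as a risk of placebo, so the contrast may be large, and then adjustment adds almost nothing. All of this stands, and it makes the point one of efficiency.

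Early stopping cuts both ways. It shrinks the gain in many settings, but it also shortens the potassium fall on placebo, which makes a very large contrast harder to assume. In a further set of Firth runs with and without stopping, the gain ranged from 0 to about 23 points and was never negative.

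A reader might infer a definite loss of 9 to 24 points on both endpoints. The documents do not support that. The range arises for the proportion under one narrow set of assumptions: baseline mean 3.9 to 4.0 and SD 0.35 to 0.45, noise 0.15 to 0.20, placebo fall 0.4 or 0.6 with SD 0.2, no change on active and no stopping. Under those assumptions time to event gains only 3 to 16 points. Gains above 16 on the proportion appear there only when subjects already below 3.5 are admitted, although the endpoint is new onset. Nor do the documents show that baseline potassium largely decides who crosses the line; likely prognostic is as far as they go.

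**Conclusion.** The omission is real, and pre-specified adjustment is the better choice. The planned tests remain valid, and the size of the loss is indeterminate. Under assumed potassium variability and placebo falls, the loss on the proportion is about 0 to 25–30 points. The top of that range needs low noise and an AUC near 0.95. The loss is near 0 when baseline is weakly prognostic (AUC 0.67) or when the arms separate about as strongly as is assumed for acidosis. It is often under 10 points once stopping at acidosis is modelled. For time to event it is usually smaller.

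All figures take 3.5 mEq/L as the cut-off. Section 12.4 speaks of significant hypokalemia without giving one, and Section 6.3.2 lists values below 3.0 separately, so another cut-off would change the numbers though not the argument. Confidence that adjustment is worthwhile is good; confidence in the size of the gain is moderate to low.

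**What to change.** In Section 12.4, before unblinding:
- **Proportion:** Firth penalized logistic regression, tested by the penalized likelihood ratio, with terms for study product, age category (youngest group pooled with 2–11 years if sparse) and baseline potassium.
- **Time to event:** a Cox model with study product and baseline potassium, stratified by age category. Name the test statistic and check its size, since the Cox score test in these runs rejected in about 4 to 7% of null trials.
- **Supportive:** keep the CMH and log-rank tests as written.
- **Covariate:** the Period 3 pre-dose potassium, or its mean with the Visit 2 and stabilization values if the assay is the same. This needs checking: the pre-dose panel goes to the central laboratory (Section 10.2.11.2), while the serial values come from the point-of-care device (Section 10.2.11.6).

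Averaging can help. Let B be the between-subject variance and E the noise variance. With k baseline readings, the residual variance of a follow-up value is B + E − B²/(B + E/k), ignoring variation in the fall. For SD 0.4 and noise 0.15, going from 1 to 5 readings takes it from 0.0422 to 0.0269, a 36% cut. For noise 0.30 it goes from 0.148 to 0.106, a 28% cut.

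The cost is SAP wording. Baseline potassium is already collected. The downside is that the estimate becomes a conditional odds or hazard ratio; the retained CMH and log-rank tests keep the unadjusted comparison in view.

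### The two log-rank tests are specified without the age strata used in randomization, the primary CMH test and the ANCOVA; the plan should state them, though the power at stake is conditional

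*Combined protocol and SAP*

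**What the plan says.** Section 12.1: "Randomization will be stratified according to the following age categories". The categories are 6 to 23 months, 2 to 11 years, and 12 years or older.

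Section 12.3: "The primary study product comparisons will be made using the two-sided Cochran-Mantel-Haenszel (CMH) test stratified by age category". Section 12.4 analyses the hypokalemia proportion in the same way. Its ANCOVA for mean changes is described as "having study product assignment and age category as factors and baseline as a covariate".

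For the two time-to-event endpoints, section 12.4 says only: "Time to first episode of metabolic acidosis and time to first episode of hypokalemia will be compared with a log-rank test". The Synopsis repeats this. No other section adds strata or an age term. Section 6.1 allows the youngest group to hold fewer than 4 subjects.

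**The concern.** When randomization is balanced within strata, an analysis that pools them overstates the variance of the treatment comparison if event risk differs between strata. The test then rejects less often than 5% under the null and loses power under the alternative. A stratified log-rank test compares the arms within each age group and avoids this.

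The documents give some reason to expect age to matter. Section 4.1.2 puts alkali need at 2-4 mEq/kg/day in adults and up to 10 in the youngest, a ratio of 10/4 = 2.5 to 10/2 = 5. Section 4.2.2 justifies staggered enrollment partly by differences in renal maturation.

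Both times are secondary efficacy endpoints, and section 12.5 places secondary efficacy endpoints under sequential gatekeeping. No effect size or power is stated for hypokalemia, so that is where an inefficient test could matter. Leaving the version of the test open would also allow the choice to be made after seeing data.

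**Working it through.** **The plan's own figure.** Section 12.1 claims: "Sixteen evaluable subjects per arm provides at least 90% power to show superiority of ADV7103 over placebo". For the assumed event rates it adds: "This calculation assumes that approximately 85% of placebo subjects and 15% of ADV7103 subjects will develop hyperchloremic metabolic acidosis". The test level is 5%, two-sided.

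Pooled normal approximation with n = 16 per arm and mean proportion 0.50:
- Null SE = √(2 × 0.5 × 0.5/16) = 0.1768
- Alternative SE = √(2 × 0.85 × 0.15/16) = 0.1262
- z = (0.70 − 1.96 × 0.1768)/0.1262 = 2.80, so power is 99.7%. Exact Fisher power is 98.4%.

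Both agree with the stated lower bound of 90%.

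**Log-rank power at the same rates.** Under proportional hazards, HR = ln(0.85)/ln(0.15) = 0.086. Expected events = 16 × 0.85 + 16 × 0.15 = 16. By Schoenfeld's formula, z = |ln 0.086| × √(16/4) − 1.96 = 2.95, so power is 99.8%. Little room is left for stratification to help.

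**Simulation A, matched to overall event rates.** 16 per arm, 6 days of follow-up, daily (tied) event times, proportional hazards within strata, 2,000 to 3,000 runs per cell. Per-arm stratum sizes (youngest/middle/oldest) were 2/5/9, 1/4/11, 2/2/12 and 4/6/6; the 60% vs 20% runs omitted 2/2/12. Only the 85% vs 15% rates come from the plan. The other rates, the hazard gradients and the stratum sizes are assumptions. Cells give power in %, unstratified / stratified, as ranges over stratum sizes.

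| Hazards, youngest:middle:oldest | 85% vs 15% (planned) | 85% vs 40% | 85% vs 50% | 60% vs 20% |
|---|---|---|---|---|
| 1:1:1 | 99.4–99.7 / 99.3–99.6 | 82.0–83.1 / 80.2–81.9 | 60.9–64.0 / 60.3–61.7 | 66.7–67.5 / 65.7–66.5 |
| 2:1.5:1 | 99.5–99.8 / 99.4–99.6 | 82.4–83.4 / 82.4–82.9 | 62.6–65.2 / 62.9–64.9 | not run |
| 4:2:1 | 99.7 / 99.6–99.8 | 84.5–87.0 / 85.7–90.3 | 63.3–69.7 / 67.6–74.9 | 66.4–67.5 / 69.1–71.9 |
| 9:3:1 | 99.8–100 / 99.9–100 | 85.3–88.0 / 90.3–95.9 | 65.2–70.4 / 74.0–86.6 | 68.1–71.2 / 75.1–81.2 |

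Comparing like with like (same stratum sizes, weaker effects), the change from stratifying is:
- equal risk: −0.6 to −2.6 points
- 2-fold: −1.1 to +0.4 points
- 4-fold: +0.8 to +5.2 points
- 9-fold: +5.0 to +16.2 points

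The Monte Carlo SE of a single power near 65% with 2,000 runs is √(0.65 × 0.35/2000) = 1.1 points, so differences of about a point are noise.

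Null rejection in the 60%-event setting, unstratified / stratified:
- equal risk: 5.1–5.4% / 4.9–5.1%
- 4:2:1: 3.1–3.4% / 4.6–5.1%
- 9:3:1: 1.5–2.7% / 4.8–5.3%

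**Simulation B, fixed hazard ratio.** 32 subjects in strata of 4/12/16, HR 0.35, daily placebo hazards as listed (all assumed), run more than once independently:
- Equal hazards: 67–68% unstratified, 64–66% stratified.
- 0.4/0.3/0.2 (2-fold): 59.6% and 60.2%.
- 0.9/0.5/0.2 (4.5-fold): 55–56% and 64–65%, a gain of about 9 points. Null rejection 3.3–3.5% and 5.4–6.0%.
- 1.2/0.6/0.15 (8-fold): 39–41% and 60%, a gain of about 20 points. Null rejection 1.8% and 5.0% in the run that recorded it.
- With only 2 subjects in the youngest stratum: 54% and 62% at 4.5-fold, 43% and 59% at 8-fold, but 59.1% and 57.6% at 2-fold.

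**The case against.** The strongest reply has five parts.

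- **The text is silent; it does not choose an unstratified test.** Section 12.4 also names a CMH test without repeating the strata, and nobody would read that one as unstratified. This stands in part. But a CMH test is stratified by construction and section 12.3 names its strata, whereas a log-rank test named without strata is ordinarily read as unstratified. Either way the sentence needs an edit.
- **The gradients are invented.** This stands. Alkali need per kg is a maintenance dose, not a hazard of crossing a threshold after withdrawal, and every subject is titrated to an age-specific bicarbonate range before randomization. For hypokalemia the threshold is the same at all ages, and the documents offer no evidence that its risk depends on age.
- **The change in acidosis threshold at 4 years.** A reader might cite this as evidence that risk differs between the strata. It is not: the cut falls inside the 2 to 11 year stratum, and the lower threshold goes with a lower target range.
- **Gatekeeping.** A reader might infer that a failed log-rank test would block later claims. Section 12.5 gives no order of testing, so what follows either endpoint is unknown.
- **Sparse strata.** A stratum with subjects in only one arm adds nothing to a stratified test, and the youngest group may be very small. This stands and shapes the fix.

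**Conclusion.** A minor specification gap, worth closing. The two log-rank tests omit the factor that governs randomization and the plan's other main comparisons.

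The loss depends on how strongly risk varies with age, which the documents do not say. Under the assumed weaker effects it is about 1 to 5 points at a roughly 4-fold difference (about 9 in the 4.5-fold, HR 0.35 scenario) and about 5 to 20 points at 8- to 9-fold. At about 2-fold it is not material.

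Two stronger readings are not supported. One is that power is lost on both endpoints whenever risk differs by age: for time to acidosis at the planned rates, both tests have about 98% power or more under every gradient in simulation A. The other is that the omission threatens validity: any error is conservative, so false positives are not inflated, and the primary CMH analysis is untouched.

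**What to change.** Before unblinding, change the sentence in section 12.4 and in the Synopsis to specify, for both endpoints, a *log-rank test stratified by age category (the randomization strata)*.

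Add a prespecified rule that pools a very sparse youngest stratum with the 2 to 11 year stratum. The trigger should be the total count in that stratum, which is known while treatment remains blinded. The plan's own target of 4 subjects is one natural cut-off.

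The cost is a short text change and, if risk does not differ by age, about 1 to 3 points of power. No change to sample size, data collection or the primary analysis is needed.

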To ensure maximum safety for the subjects who may experience a decline in serum potassium, repeat serum potassium measurements should be performed 2-4hrs (and not 24hrs) after the first measurement if serum potassium is found to be below 3.5 mEq/L or to have decreased by more than 15 percent since the last measurement. Potassium (potassium hydrochloride) will be supplemented, as needed, for levels falling below 3.0 mEq/L.

If a subject's serum bicarbonate level becomes < 18 mEq/L for subjects ≥ 4 years old or < 17 mEq/L for subjects < 4 years old (study definition of metabolic acidosis), another serum bicarbonate result will be obtained within 2-4 hours or earlier if subject safety requires immediate intervention. If the repeat serum bicarbonate result confirms metabolic acidosis, the subject will have achieved the primary endpoint. If the second level is above the threshold, the subject will continue her/his current study product assignment and resume the regular schedule of blood sample collections. Subjects who develop metabolic acidosis during the Withdrawal Period will be discontinued from study product in a blinded fashion and begin taking active ADV7103 at the next scheduled dosing time point (unless subject safety requires immediate intervention) at their pre-randomization dose.

They will remain under investigator monitoring for approximately 6 days or until the metabolic acidosis (and any accompanying hypokalemia, if applicable) is corrected, whichever is longer. The frequency of laboratory evaluations for subjects who require correction of serum bicarbonate and/or potassium will be determined by the Investigator.

Potassium supplementation initiated during Period 3, if applicable, should be stopped at restoration of ADV7103 dosing..

If restoration of ADV7103 at the pre randomization dose fails to restore targeted serum bicarbonate levels, the dose of ADV7103 will be increased to achieve this objective as long as it is tolerated. In order to maintain serum potassium levels ≥ 3.0 mEq/L, the dose of ADV7103

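### Section 12.4 has no rule for the switch to open-label ADV7103, so the LOCF changes in serum bicarbonate and potassium can largely compare drug with drug, and the hypokalemia proportion is hard to interpret

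*Combined protocol and SAP*

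**What the plan says.** On the switch, Section 6.2.3 states: "Subjects who develop metabolic acidosis during the Withdrawal Period will be discontinued from study product in a blinded fashion and begin taking active ADV7103". These subjects stay under observation for about 6 days or until the acidosis is corrected, and Section 10.2.18 keeps them in Period 3 for that time. Section 9.2 describes this part of Period 3 as open-label. Section 10.2.11.2 calls for a chemistry panel, including bicarbonate and potassium, on the last day of Period 3.

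On how common it will be, Section 12.1 states: "This calculation assumes that approximately 85% of placebo subjects and 15% of ADV7103 subjects will develop hyperchloremic metabolic acidosis". Since confirmed acidosis triggers the switch, these are also the expected switch rates.

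On the analysis, Section 12.4 says that mean changes in serum bicarbonate, serum potassium and the two urine ratios "will be compared at a last observation carried forward (LOCF) endpoint with an analysis of covariance model". For potassium events it says: "The proportion of subjects with significant hypokalemia up to Day 6 of Period 3 will be similarly analyzed with a CMH test". Time to first hypokalemia gets a log-rank test with no stated censoring rule.

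The only cut-off resembling a stop rule is in Section 12.3. There, bicarbonate values count to Day 6 or early discontinuation, and the text does not say whether that means leaving product or leaving the study. The additional analyses in Section 12.6 do not mention the switch. Section 12.2 analyses safety by the product actually received, with no rule for subjects who take both products within Period 3.

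**The concern.** The withdrawal design creates a drug-placebo contrast and then removes it, subject by subject, once acidosis is confirmed. An analysis that carries forward the last Period 3 value without regard to the switch would take, for most placebo subjects, a value measured while ADV7103 is restoring bicarbonate and potassium. A large true effect could appear small, and if these changes sit in the Section 12.5 gatekeeping sequence, a spurious failure could block later tests.

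The hypokalemia proportion has a related problem. The arms differ greatly in time spent on randomized product, and an ever/never count does not allow for that. Neither way of counting compares ADV7103 with placebo over equal time.

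**Working it through.** **The plan's own figure.** Section 12.1 states that "Sixteen evaluable subjects per arm provides at least 90% power to show superiority of ADV7103 over placebo", at 85% against 15% and the two-sided 5% level. With 16 per arm the normal approximation gives 99.7%. Exact enumeration in a single stratum gives 99.5% for the CMH test and 98.4% for Fisher's test. The stated lower bound is met.

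**Expected switches.** Placebo: 16 x 0.85 = 13.6. ADV7103: 16 x 0.15 = 2.4. The probability that at least 12 of 16 placebo subjects switch is 92%.

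**LOCF contrast.** Let r be the share of the withdrawal effect reversed by the last sample. The documents give no value, so a range is shown. If switchers and non-switchers on placebo would have had the same mean fall, and the few ADV7103 switchers are ignored, the contrast kept is 1 - 0.85r. The power column takes an endpoint that would have 90% power at 16 per arm (standardized difference 1.15), with the SD unchanged.

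| r (assumed) | Contrast kept | Power, from 90% |
|---|---|---|
| 0.25 | 79% | 72% |
| 0.5 | 58% | 46% |
| 0.75 | 36% | 22% |
| 1 | 15% | 7% |

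For a very large effect (standardized difference 2), power is 99%, 90%, 54% and 13% at the same values of r. Restricting LOCF to pre-switch values removes the factor: the contrast kept returns to 1.

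**Time on randomized product.** Treat 85% and 15% by Day 6 as constant hazards (assumed).
- Hazards: -ln(0.15)/6 = 0.316 per day on placebo; -ln(0.85)/6 = 0.0271 on ADV7103.
- Mean time to switch or Day 6, (1 - exp(-6h))/h: 0.85/0.316 = 2.7 days; 0.15/0.0271 = 5.5 days.

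**Hypokalemia proportion, stopped at the switch.** Give both arms the same hypokalemia hazard k (assumed), so that there is no true difference. The crude proportion is k/(k + h) x (1 - exp(-6(k + h))).

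| k per day | Placebo | ADV7103 |
|---|---|---|
| 0.05 | 12% | 24% |
| 0.1 | 22% | 42% |
| 0.2 | 37% | 66% |

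In simulation with 16 per arm and no stratification, the CMH test on these proportions falsely rejects in about 20% (k = 0.1) and 37% (k = 0.2) of trials, almost always showing ADV7103 as worse. A log-rank test censored at the switch rejects in 5 to 6%. The simulation takes the two hazards as independent.

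**Hypokalemia proportion, all data to Day 6.** With k = 0.2 before and after the switch, both arms give 1 - exp(-1.2) = 70%, so there is no bias under equal hazards. If ADV7103 does lower the risk, placebo is diluted. A daily model with acidosis hazard 0.271 and placebo hypokalemia hazards of 0.05 to 0.20 gives these placebo proportions:
- six full days on placebo: 26.5% to 73.8%;
- all data to Day 6, half the risk remaining after the switch: 20.7% to 62.4%;
- stopped at the switch, or no risk remaining after it: 14.5% to 46.1%.

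**The case against.** The best defence is that the plan may already intend the right cut-off. Section 6.2.3 describes the switch as discontinuing product, Section 12.3 stops at early discontinuation, and Section 12.4 analyses hypokalemia in a similar way to the primary endpoint. Using LOCF at all suggests that observation was meant to end at discontinuation. That reading is possible. However, Section 12.3 covers bicarbonate in the primary analysis only and leaves its term undefined, and nothing in Section 12.4 ties the LOCF value to randomized product.

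It is also fair that full reversal is a worst case, since subjects who switch on Day 5 or 6 may not be corrected by the last sample; hence the range for r. Changes in serum bicarbonate and potassium are analysed in Section 12.4 but are not among the endpoints listed in Section 6.3.2, which limits their weight.

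Three stronger conclusions that a reader might draw are not supported.

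- That every secondary analysis is exposed. Time to acidosis and failure to hold bicarbonate at 18 or 17 mEq/L are settled at or before the switch. So, in switchers, are two values below the lower limit of normal, if that limit is at least 18 or 17.
- That the hypokalemia proportion is biased against ADV7103 because the analysis does not stop at the switch. Post-switch data can only add placebo cases to an ever/never endpoint. The 37% against 66% pattern arises when counting does stop there. The equal hazard behind it is a device to isolate the time effect, not a likely rate.
- That post-switch safety events would be credited to placebo. Section 12.2 assigns safety by product actually received, which points the other way. What is missing is an attribution rule within Period 3.

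**Conclusion.** The point stands for the LOCF changes in serum bicarbonate and potassium. Read literally, Section 12.4 keeps 79% to 15% of the drug-placebo contrast for r from 0.25 to 1. This rests on the plan's 85% switch rate, an assumed r, and similar falls in placebo switchers and non-switchers.

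For hypokalemia the conclusion is narrower. The crude proportion does not compare the arms over equal time under either counting rule, and the plan does not say which applies. Stopping at the switch leaves placebo with about half the time at risk and can disfavour ADV7103. Counting everything to Day 6 dilutes the placebo rate if ADV7103 lowers the risk.

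The urine ratios are less exposed if sampled only on Days 1 and 2, as Section 10.2.11.3 states. Section 10.3.3.2 and the spot-urine footnote in Section 17.1 describe sampling on each day of Period 3, and these passages must be reconciled.

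The primary analysis and its power are unaffected. This should be corrected before unblinding, but it does not threaten the main result.

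**What to change.** 1. In Section 12.4, define the LOCF value as the last value before the first dose of open-label ADV7103 or other alkali.
2. In Section 12.3, define early discontinuation as the end of randomized product.
3. Censor the already planned log-rank test for hypokalemia at the switch and stratify it by age category. Interpret the hypokalemia comparison from it, and show the proportion descriptively beside time at risk in each arm.
4. Tabulate Period 3 adverse events and potassium flags after the switch separately as open-label ADV7103, in line with Section 12.2.

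The cost is analysis wording only, with no change to trial conduct. There are two limits to report. Censoring at the switch may be informative, because acidosis and potassium are related. And a switcher's last pre-switch bicarbonate is the low value that triggered the switch, so the LOCF change describes withdrawal up to that point and not the state at Day 6.
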